### 7.5 Reporting AEs and SAEs

1. All AEs will be recorded on AE case report forms at the research site
2. Site staff should report any SAE *immediately* to the Chief Investigator. Upon receipt of the SAE report the Chief Investigator must:
  - a. All SAEs: Immediately inform the Sponsor (within 1 working day)
    - i. Inform the REC on behalf of the Sponsor as soon as possible, and no later than fifteen calendar days for non-fatal and non-life threatening SAEs

- b. *Unexpected SAEs related to a study procedure (SUSAR – suspected unexpected serious adverse reaction):*
  - i. Inform the REC on behalf of the Sponsor as soon as possible, and no later than one calendar day for fatal or life-threatening SAEs.
  - ii. Convene a meeting of the Chief Investigator and study investigators as soon as possible, and no later than:
    1. Fifteen calendar days for fatal or life-threatening SAEs
    2. Thirty calendar days for non-fatal and non-life-threatening SAEs

### **7.6 Pregnancy**

Pregnancy is associated with a diverse range of physiological changes, and can therefore be expected to greatly influence both activity and physiological monitoring data. Pregnancy is thus an exclusion criterion for this study.

Where pregnancy in a female participant becomes apparent after the enrolment of the participant to the study, this must be recorded as an adverse event. The participant's referring rheumatologist and GP must be informed, and then the participant must be discharged from the study.

## **8. DATA ANALYSIS**

### *8.1 Correlation between DAS28 and RADAI-5 measurements*

The correlation between paired DAS28 and RADAI-5 measurements taken at each study visit will be assessed by Pearson and Spearman correlation coefficients. DAS28 and RADAI-5 scores will also be dichotomised to binary disease activity values (e.g. high disease activity vs remission/low/moderate disease activity) based on published thresholds, and agreement between categorisation by DAS28 vs RADAI-5 scores assessed by Cohen's kappa statistic.

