## 2. STUDY SUMMARY

[figure not shown]
Trial Title	Remote monitoring of disease and physical activity in rheumatoid arthritis: a pilot study
Summary of Study Design	Observational longitudinal cohort study
Summary of Participant Population	Participants with established rheumatoid arthritis with active disease commencing a new disease-modifying anti-rheumatic drug
Planned Sample Size	20 participants
Planned Number of Sites	1
Follow Up Duration	3 months
Planned Study Period	11 months
Primary Objectives	To demonstrate the feasibility of remote disease activity monitoring in participants with rheumatoid arthritis, to support a future clinical efficacy trial.
Primary endpoint:	Correlation and agreement of remote methods of disease activity measurement (patient reported outcome measures, and activity/gait/cardiorespiratory monitors) compared to face-to-face assessments of disease activity in 28 joints with C-reactive protein (DAS28-CRP) scores.
Study Intervention:	Nil (standard clinical care, observational only)

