### 4.2 Primary objectives

1. To assess the correlation and agreement between paired DAS28 and RADAI-5 measurements
2. To assess the longitudinal responsiveness and minimal detectable change in repeated RADAI-5 measurements
3. To assess the acceptability of remote PROM capture and activity/gait/heart rate monitoring, through the use of participant questionnaires and focus groups

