### 4.3 Secondary objective

1. To use validated algorithms and novel machine-learning methods to identify activity, gait and heart rate monitor signatures that correlate with, and are predictive of, DAS28- and RADAI-5-defined disease activity

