## **6. STUDY VISITS**

### 6.1 Initial study visit

Participants attending their initial appointment will undergo the following procedures.

1. All participants will have the opportunity to discuss the study further with a study investigator before signing the consent form.
2. Participant eligibility for study enrolment based on the inclusion and exclusion criteria will be confirmed.
3. Participants will be asked to provide baseline information including age, sex, address, telephone number, email address, past medical history, Clinical Frailty Score,[12] Charlson Comorbidity Index,[13] current medications, smoking status and alcohol intake.
4. The participant's height and weight will be recorded.
5. A researcher will then examine the participant to ascertain the 28-joint tender and swollen counts, a patient visual analogue scale, and a physician visual analogue scale, required to assess disease activity using the DAS28-CRP score (Appendix A).
6. The participant will then complete a RADAI-5 questionnaire (Appendix D).
7. The participant will then be asked to complete the following paper questionnaires:
  - a. Health Assessment Questionnaire Disability Index (HAQ-DI)
  - b. FACIT-F and MFS
  - c. PHQ-2
  - d. EQ-5D-5L
8. Participants will then be shown how to access the ePROMs portal. Written information will be provided to participants to explain this further.
9. Participants will then be instructed on how to wear and activate the remote monitoring digital tracker devices. Written information will be provided to explain this further. The following devices will be provided, and should be worn simultaneously for 7 days following the study visit:
  - a. Axivity AX6 monitor and adhesive dressing – for application to lower back
  - b. Axivity AX6 monitor and wrist strap – for application to wrist
  - c. VitalPatch self-adhesive monitor – for application to left upper chest wall
  - d. A study mobile phone and charger – for data linkage and downloading from the VitalPatch device

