#### *6.4 ePROMs remote capture and review*

1. All participants will be asked to complete a RADAI-5 questionnaire via the secure online ePROMs portal once every week for the 12 week follow-up duration of the study
2. Automated weekly reminder emails will be sent via the ePROMs platform to participants to remind them to complete a RADAI-5 assessment.
3. ePROMs RADAI-5 data will be reviewed at each monthly visit, and any missing data discussed with the participant to identify any difficulties in accessing or using the ePROMs platform.

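### The primary endpoint concerns remote measurement, but the stated RADAI-5/DAS28 correlation and kappa use the form completed at the clinic visit, not the weekly portal entry

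*Protocol*

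**What the plan says.** **Endpoint.** The primary endpoint row of Protocol Section 2 reads "Correlation and agreement of remote methods of disease activity measurement (patient reported outcome measures, and activity/gait/cardiorespiratory monitors) compared to face-to-face assessments", the face-to-face assessment being DAS28-CRP.

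**Objectives.** The first primary objective in Section 4.2 is "To assess the correlation and agreement between paired DAS28 and RADAI-5 measurements"; it does not mention remote capture. The monitors appear in Section 4.2 only under acceptability (objective 3). Their relation to disease activity is the secondary objective in Section 4.3, which begins "To use validated algorithms and novel machine-learning methods to identify activity, gait and heart rate monitor signatures".

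**Data collection.** Section 6.4 asks participants to "complete a RADAI-5 questionnaire via the secure online ePROMs portal once every week" during the 12 weeks of follow-up, with automated email reminders. Separately, Sections 6.1 to 6.3 and the schedule in Section 15 place a RADAI-5 at each of the four visits.

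**Analysis.** Section 8.1 states: "The correlation between paired DAS28 and RADAI-5 measurements taken at each study visit will be assessed by Pearson and Spearman correlation coefficients". It adds Cohen's kappa on dichotomised scores. Section 8.2 smooths longitudinal RADAI-5 by Loess and judges it against the DAS28 minimal detectable change and EULAR response, without saying whether portal or visit scores are meant. Section 8.3 is an exploratory search for monitor signatures related to activity as defined by DAS28 and RADAI-5.

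**The concern.** The pilot's stated purpose is to show that remote disease activity monitoring is feasible, in support of a later efficacy trial. The number most likely to be carried forward is the correlation or kappa of the remote questionnaire with DAS28. Section 8.1 does not produce it. It pairs DAS28 with a questionnaire completed in the clinic at the same attendance, after a researcher has counted the joints and the patient has given a visual analogue score. That tells the reader how RADAI-5 behaves as a questionnaire in clinic. It does not tell the reader how it behaves when entered at home through the portal. Someone could follow 8.1 to the letter, report the result under the Section 2 endpoint, and leave the remote-questionnaire part of that endpoint unanswered.

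A second inconsistency concerns the monitors. Section 2 counts them in the primary endpoint, for both correlation and agreement. Sections 4.3 and 8.3 give them a secondary, exploratory role, and no agreement statistic is named for them.

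**Working it through.** The sample size is set by resources and Section 5.4 says the study is not powered, so there is no planned figure to reproduce. The check compares sections and counts pairs.

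**Step 1: which RADAI-5 does 8.1 use?** It uses "paired DAS28 and RADAI-5 measurements taken at each study visit". The order of procedures identifies that form:

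- Initial visit (6.1): joint counts and visual analogue scales are item 5, RADAI-5 is item 6, and the portal is first demonstrated at item 8. The visit 1 form therefore precedes any portal use.
- Weeks 4 and 8 (6.2) and week 12 (6.3): joint counts are item 4, RADAI-5 is item 5, and review of the remotely entered RADAI-5 is a separate item 6.
- Schedule (Section 15): RADAI-5 and review of the ePROMs record are separate rows.

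The visit form and the portal entry are two data streams, and 8.1 names the first.

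**Step 2: where does the portal stream meet DAS28?** Section 9 rejects paper capture of the weekly scores partly because they must be linked to DAS28 in real time, so the link is intended. Each analysis section can be checked for it:

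| Section | Remote data used? | Set against DAS28? | Statistic |
|---|---|---|---|
| 8.1 | No, visit RADAI-5 | Yes | Pearson, Spearman, kappa |
| 8.2 | Not stated | Yes, by change criteria | No correlation or kappa |
| 8.3 | Yes, monitors | Yes, exploratory | Correlation and prediction, no agreement statistic |
| 8.4 | Feedback on remote tools | No | Descriptive |

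No row gives a correlation or kappa of portal RADAI-5 with DAS28.

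**Step 3: counts.** Inputs are 20 participants (Section 2), four visits (Section 15) and 12 weekly entries (Section 6.4). All results are maxima under full adherence and no dropout; the protocol gives no rate for either.

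- Clinic pairs feeding 8.1: 20 × 4 = 80.
- Planned portal entries: 20 × 12 = 240, of which 0 enter the 8.1 correlation or kappa.
- Portal pairs if each follow-up DAS28 is matched to a preceding portal entry: 20 × 3 = 60 (weeks 4, 8 and 12). Allowing the first entry after day 0 to stand for baseline would restore 80.

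**Step 4: status of the monitors.** Section 2 makes their correlation and agreement with DAS28 primary. Section 4.2 makes only their acceptability primary. Section 4.3 makes their relation to DAS28 secondary, and 8.3 calls that analysis exploratory. These cannot all stand.

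**The case against.** The strongest defence is that 8.1 does what primary objective 1 asks. That objective pairs DAS28 with RADAI-5 and does not say remote. A same-visit pair is also a proper criterion-validity comparison, particularly in people starting a new DMARD whose disease activity may move within days. This stands: the same-visit analysis deserves to be kept, and part of the conflict lies between Section 2 and Section 4.2. It does not remove the mismatch, because Section 2 defines the endpoint in terms of remote methods.

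A second defence is that pairing rules belong in a statistical analysis plan. That holds for the width of a window. It does not hold for the data source, which 8.1 fixes.

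Several stronger readings are tempting and are not supported:

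- *That remote monitoring is never tested against DAS28.* Section 8.3 relates the monitors to DAS28-defined activity, and 8.2 may use portal scores.
- *That the clinic result must overstate remote performance.* This is plausible, but the documents give no data on direction or size, and the home entries are prompted by weekly emails.
- *That complete non-use of the portal would go unnoticed.* Missing entries are discussed at each follow-up visit, and acceptability is itself a primary objective. Only the 8.1 result would be unaffected.
- *That the best of many monitor correlations will be reported as primary.* Nothing in Section 8 says so; the analysis is labelled exploratory. The fault is the wording of the Section 2 row.

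**Conclusion.** The point holds in this form: the stated correlation and kappa of RADAI-5 with DAS28 rest on up to 80 clinic pairs and on none of the up to 240 remote entries, so they do not answer the remote-questionnaire part of the primary endpoint in Section 2. Section 8.2 leaves its RADAI-5 source open, and the monitors are primary in one section and secondary or exploratory in two others. The conclusion rests on reading the visit RADAI-5 as distinct from the portal entry, which the order of procedures and the schedule support. How much the clinic and remote results would differ cannot be derived from the documents. That the study is a small, unpowered pilot limits the consequences, but its purpose is estimation, and this is the estimate that its primary endpoint names.

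**What to change.** 1. In Section 8.1, for the remote-questionnaire part of the primary endpoint, pair DAS28-CRP with the portal RADAI-5 nearest the visit within a fixed window, for example the last entry in the 7 days before the week 4, 8 and 12 visits. Keep the same-visit clinic pair alongside it as the criterion-validity comparison.
2. Add agreement between clinic and portal RADAI-5. Both are on the same 0 to 10 scale, so Bland-Altman limits and an intraclass correlation coefficient apply.
3. State in Section 8.2 whether portal scores, visit scores or both are used.
4. Remove the activity, gait and cardiorespiratory monitors from the primary endpoint row in Section 2, so that it matches Sections 4.2, 4.3 and 8.3.

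**Cost.** Wording and analysis only; both RADAI-5 streams are already collected. The portal analysis has at most 60 pairs instead of 80, and fewer where entries are missed. A gap of up to 7 days can mix true change on a new DMARD with remote-capture error, and the clinic-versus-portal comparison carries the same mixture. A week 12 visit late in its window (day 84 + 7 = 91) may also fall after the twelfth weekly entry, so the window rule should say what happens then.

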### *5.4 Target recruitment size*

This is a pilot study, designed to support a future definite clinical efficacy trial. As such this pilot study is not statistically powered, but rather is intended to provide preliminary data to estimate the feasibility and acceptability of remote monitoring in patients with RA, and generate an exploratory dataset for derivation of putative digital biomarkers of arthritis activity. A target of 20 participants will be recruited to the study, based upon the limited available resources for purchasing monitoring equipment in this small pilot study.

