## APPENDIX A: THE DISEASE ACTIVITY IN 28 JOINTS C-REACTIVE PROTEIN (DAS28-CRP) SCORE

The DAS28-CRP score[1] is calculated using the following parameters:

1. Swollen (SJC28) and tender (TJC28) 28 joint counts\*
2. C-reactive protein (CRP, mg/L)
3. Patient global health assessment (VAS) (visual analogue scale, 0mm = best, 100mm = worst)

$$\text{DAS28 (CRP)} = 0.56\sqrt{\text{TJC28}} + 0.28\sqrt{\text{SJC28}} + 0.36\ln(\text{CRP[mg/l]}+1) + 0.014(\text{VAS[mm]}) + 0.96$$

\* = Where the 28 joints include the bilateral proximal interphalangeal joints, metacarpophalangeal joints, wrists, elbows, shoulders and knees.

Where CRP is below detectable levels, a value of zero will be used for the DAS28-CRP calculation.

The DAS28-CRP score has validated disease activity thresholds [2,3]:

Disease activity	DAS28-CRP threshold
Remission	< 2.4
Low	2.4 ≤ score ≤ 2.9
Moderate	2.9 < score ≤ 4.6
High	> 4.6

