#### APPENDIX D : RHEUMATOID ARTHRITIS DISEASE ACTIVITY INDEX 5 (RADAI-5)

The RADAI-5[1] is a self-completed questionnaire consisting of the following five questions, each scored on a 0-10 integer scale:

1. How active was your arthritis in the last six months? (anchors: 0 = completely inactive, 10 = extremely active)
2. How active is your arthritis today with respect to joint tenderness and swelling? (anchors: 0 = completely inactive, 10 = extremely active)
3. How severe is your arthritis pain today? (anchors: 0 = no pain, 10 = unbearable pain)
4. How would you describe your general health today? (anchors: 0 = excellent, 10 = extremely bad)
5. Did you experience joint (hand) stiffness on awaking yesterday morning? If yes, how long was this stiffness? (anchors: 0 = no stiffness, 10 = stiffness the whole day)

The mean value gives an overall “RADAI-5 score”, with validated disease activity thresholds[2]:

Disease activity	RADAI-5 thresholds
Remission	0.0-1.4
Mild	1.6 – 3.0
Moderate	3.2 – 5.4
High	5.6 – 10.0

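### Section 8.1 measures DAS28/RADAI-5 agreement only by kappa on a binary split, and the correlations planned for the full scores do not show individual error; prediction limits and the full category table would be a cheap addition

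*Protocol*

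**What the plan says.** The Study Summary gives the primary endpoint as "Correlation and agreement of remote methods of disease activity measurement" against face-to-face DAS28-CRP. Primary objective 1 in section 4.2 narrows this to the two scores: "To assess the correlation and agreement between paired DAS28 and RADAI-5 measurements".

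Section 8.1 supplies one method for each half. For correlation, the pairs taken at each study visit "will be assessed by Pearson and Spearman correlation coefficients". For agreement, both scores are split in two and "agreement between categorisation by DAS28 vs RADAI-5 scores assessed by Cohen's kappa statistic". The split is given by example: "e.g. high disease activity vs remission/low/moderate disease activity".

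Section 8.2 sets RADAI-5 against the published minimal detectable change in DAS28 and the EULAR response criteria. That concerns change over time, not closeness in level. Nowhere does the protocol name a residual SD, prediction limits or a calibration analysis for the undivided scores.

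Appendix A states "The DAS28-CRP score has validated disease activity thresholds": remission below 2.4, low up to 2.9, moderate up to 4.6, high above 4.6. RADAI-5 (Appendix D) is the mean of five items, "each scored on a 0-10 integer scale", with its own four bands. On size, section 5.4 says "A target of 20 participants will be recruited to the study" and that the study is not powered.

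**The concern.** Remote monitoring is applied one patient at a time, so the useful question is how wrong a single RADAI-5 score can be about that patient's DAS28. The two planned statistics leave this largely unanswered.

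- **Kappa on the example split.** Remission, low and moderate are pooled. A patient in remission whom RADAI-5 calls high counts the same as one near the top of moderate whom it calls high. A pair that is remission on one score and moderate on the other counts as agreement.
- **Pearson and Spearman.** Neither changes if one score is shifted or rescaled by a positive factor, and both rise with the spread of disease activity among those recruited. Section 5.1 sets no minimum DAS28 and admits patients from 4 weeks before to 8 weeks after starting a drug, so the spread is not controlled.

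At stake is how the pilot's result is read when it is used to support a definitive trial. A correlation could look strong while the error for an individual remains wide against the Appendix A bands.

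**Working it through.** The protocol states no expected r, SD or power, so there is no figure of its own to reproduce. The check asks what a given r implies for one patient.

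**Inputs.** From Appendix A: remission below 2.4, high above 4.6, gap 4.6 − 2.4 = 2.2. Assumed, because the protocol gives neither: DAS28 SD of 1.0, 1.2 or 1.4, and r from 0.5 to 0.9. The relation is taken as linear and roughly normal, with one pair per person and a large sample.

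**1. Width of the range.** Half-width of the 95% range of DAS28 at a given RADAI-5 = 1.96 × SD × √(1 − r²). For example, SD 1.2 and r = 0.8 give 1.96 × 1.2 × 0.6 = 1.41.

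| SD | r = 0.5 | r = 0.7 | r = 0.8 | r = 0.9 |
|---|---|---|---|---|
| 1.0 | ±1.70 | ±1.40 | ±1.18 | ±0.85 |
| 1.2 | ±2.04 | ±1.68 | ±1.41 | ±1.03 |
| 1.4 | ±2.38 | ±1.96 | ±1.65 | ±1.20 |

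**2. The r needed for a full width below 2.2.** r > √(1 − (1.1 / (1.96 × SD))²), which is 0.83, 0.88 and 0.92 for SD 1.0, 1.2 and 1.4.

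**3. Where the range touches both remission and high.** At r = 0.8 and SD 1.2 the predicted DAS28 must lie between 4.6 − 1.41 = 3.19 and 2.4 + 1.41 = 3.81, a window of 0.62. At the centre, 3.5, the range runs from about 2.1 to 4.9. The residual SD is 1.2 × 0.6 = 0.72, so 1.1 / 0.72 = 1.53 SDs separate 3.5 from each cut-off. That leaves about 6% of patients in remission and 6% in high. At r = 0.7 it is about 10% in each; at r = 0.9, about 2%.

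**4. Dependence of r on spread.** Hold the residual SD at 0.85, so the individual error is always ±1.96 × 0.85 = ±1.67. With DAS28 SD 1.0, r = √(1 − 0.85²) = 0.53. With SD 1.4, r = √(1 − (0.85/1.4)²) = 0.79. The coefficient improves greatly and the accuracy not at all.

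**5. Small sample.** Fitted on 20 people with one pair each (t on 18 df, factors √(19/18) and √(1 + 1/20)), the full width at SD 1.2 becomes 3.79, 3.18 and 2.31 at r = 0.7, 0.8 and 0.9. An observed r of 0.8 from 20 independent pairs has a 95% interval of about 0.55 to 0.92.

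**The case against.** The plan does not contradict itself. It promises correlation and agreement and names a method for each, and it nowhere says that r will be read as agreement. A reader might infer that the primary objective has no agreement analysis. That is not so: kappa on published categories is a recognised choice when two scores are on different scales and raw differences mean nothing. It does cross-classify individuals, and the split is only an example, so a remission cut is not ruled out. An unseen SAP could also add score-scale analyses.

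A reader might also infer that a high r would trigger the next trial. The protocol sets no threshold on r and no go/no-go rule, and it describes the study as unpowered and preliminary. Nor can one say that a high r in general conceals an error running from remission to high activity. At r = 0.9 the range no longer reaches both categories when the SD is 1.2 or less (large-sample calculation). At r = 0.8 and SD 1.2 it does so only inside the 0.62-point window. If predicted values are normal with SD 0.8 × 1.2 = 0.96, about 25% of patients fall in that window when the mean is 3.5, and about 15% when it is 4.5.

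All of this stands, and it limits the point. What remains is that the one agreement measure named is binary, that its example cut pools three categories, and that neither the correlations nor section 8.2 estimates individual error in level.

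**Conclusion.** The point holds as a worthwhile improvement. Section 8.1 answers the agreement part of a primary objective in coarse form only, and individual error on the DAS28 scale is never estimated although the pairs to estimate it will be collected.

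The size is conditional. For assumed SDs of 1.0 to 1.4, r must exceed roughly 0.83 to 0.92 before the 95% range for one patient is narrower than the remission-to-high gap. A range that reaches both extremes is confined to mid-range predictions. These figures rest on assumed SD and r, linearity and approximate normality; the 2.2-point gap is the only input from the protocol. They show why r alone is hard to interpret. They do not show that RADAI-5 performs badly.

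**What to change.** Keep the correlations, labelled as association, and kappa, labelled as category agreement. Add to section 8.1:

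1. A regression of DAS28-CRP on RADAI-5 with a random intercept for each participant, since each person contributes up to four visit pairs.
2. The total residual SD (between- and within-participant components combined) with its confidence interval.
3. The 95% prediction limits of DAS28-CRP for one person at RADAI-5 1.4, 3.0 and 5.4, the upper bounds of the remission, mild and moderate bands in Appendix D, set against the Appendix A bands.
4. The full four-by-four table of DAS28-CRP category by RADAI-5 category, so that remission-versus-high pairs are visible.

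The cost is a few lines of text, one model and one table, with no new data. With 20 participants the limits will be imprecise and should be reported as such. They will also look less favourable than a correlation coefficient.
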